9.2. Safety Set

The safety set includes all patients who received a treatment and analysis is focused on the treatment actually performed.

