10.2. Handling of Withdrawals and Dropouts

Withdrawn subjects will be evaluated in the FAS and safety set. Missing values are imputed as mentioned in Section 10.1.

Subjects with premature study discontinuation before end of the efficacy assessment period (i.e. before the 12 weeks follow-up post wound closure confirmation) lead to problems for analyses which include data from re-admissions. If a subject discontinued study participation during the efficacy assessment period, it is not known whether the subject had a(nother) readmission and data are missing. Consequently, the corresponding variables will be set to missing for all those subjects except for "Lost-to-follow-ups" who completed the eschar

removal treatment. The exception is done under assumption that subjects who are lost to follow up would have come back for re-admission if this had been necessary (Without this exception a lot of information would have been lost in MW2010 since the percentage of subjects with readmission is higher for "Lost-to-follow-ups" then for the rest of the population).

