EQ-5D-Y consists of 5 items with 3 possible answers each. It will be evaluated per the EQ-5D-Y user guide [20]. Note that for children aged 2 – 11 years, the parent/caregiver will complete a proxy version of the EQ-5D for the patient, children aged 12-18 will complete the

questionnaire themselves. EQ-5D will not be assessed for children younger than 2 years (based on age of first FU visit).

For each item, relative and absolute frequencies of the answers will be computed in total and per age group, defined in the stratification variables (see Section 11.1.11). The table will be presented by treatment arm and overall. The analysis will be done per age at randomization. Furthermore, summary statistics of the EQ VAS will be computed in total and per age group. The table will be presented by treatment arm and overall.

The EQ-5D states will be converted to a single summary index using the USA value set from [21]. For subjects with incomplete questionnaires, the summary index will be a missing value.

Immunogenicity Evaluation

The immunogenicity evaluation will be done in a separate analysis and is described in a separate document.

Pyrexia and Hypothermia

Pyrexia (and related terms) and hypothermia reported as AEs will be presented in the AEs tables.

Systemic Infection

Systemic infections reported as AEs will be presented in the AEs tables.

Adverse Events

Counts and frequencies of subjects reporting treatment emergent adverse events (TEAEs), related TEAEs, and serious TEAEs per treatment arm will be computed per system organ class (SOC) and preferred term (PT). This will be done separately by:

- Severity (mild / moderate / severe AEs)
- Relatedness (not related or remotely related / possibly related or probably related or related AEs)

Time of onset (during the treatment session / within 24 hours after treatment / 24 – 72 hours after treatment / more than 72 hours up to the end of the first week after treatment / during week 2 to week 4 after treatment / more than 4 weeks after treatment)

Note: During the treatment session is defined as the time frame from start date/time of first eschar removal procedure to end date/time of last eschar removal procedure.

All serious adverse events will be listed for the enrolled population.

For more details see Section 11.1.5.4.

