For each of the two stages of analysis (see Section 11 for details), the safety data gathered in that stage will be analyzed separately. That is, in the first stage analysis (acute + 12M follow-up), all AEs reported until the 12 months follow-up will be analyzed separately for the following sub-periods: 1) until the 12 weeks follow-up, 2) between the 12 weeks follow-up and the 12 months follow-up (including AEs from the first sub-period that are still ongoing), 3) combined until the 12 months follow-up. In the second stage analysis (24 months follow-up), all AEs reported between the 12 months follow-up and the 24 months follow-up (including AEs from the first stage that are still ongoing) will be analyzed. Furthermore, a combined analysis, including all reported AEs, will be provided at the end of the trial.

Central Laboratory Values

For all analyses involving data from the central laboratory only samples taken within the allowed time range are considered

- Pre procedure: Within 12 hours before start of the procedure until up to 15 min after start.
- Post procedure: Within 24 hours after end of the procedure

Samples not taken in the allowed time range are excluded from the analysis.

Imputation of data from the central laboratory is only done for planned missing values. Version 10.01 of the study protocol specifies some planned missing laboratory samples. On the one hand, a laboratory sample before the additional application of NexoBrid is not required. On the other hand, a laboratory sample before a nonsurgical procedure is only prescribed for the first eschar removal procedure and a laboratory sample after a nonsurgical procedure is only

required for the last eschar removal procedure. To enable analysis of pre-post differences on procedure level, the planned missing values are imputed as follows:

- Planned missing measurements before an additional application / a non-surgical procedure
 - Values of a sample taken after the previous eschar removal procedure are used if the laboratory sample was taken within 12 hours before start of the eschar removal procedure.
- Planned missing measurements after a non-surgical procedure
 Values of a sample taken before the subsequent eschar removal procedure are used if the laboratory sample was taken within 24 hours after end of the nonsurgical procedure.

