11.1.5. Safety Analyses

All safety variables except for the first safety endpoint "time to reach complete wound closure", which will be evaluated using the FAS, will be evaluated on the safety set.

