11.2.4.4. Adverse Events

The analyses of Adverse Events described in Section 11.1.5.4 will be repeated, as deemed relevant, on the following additional sub-periods:

- adverse events occurring after the 12 months follow up (including AEs from the first stage that are still ongoing);
- o adverse events occurring during the entire study period

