The formula for total number of events D is: $D = \frac{4(z_{\alpha} + z_{\beta})^2}{(\ln \lambda)^2}$

(Piantadosi, Clinical Trials: A Methodologic Perspective, p.169)

 $z_{\alpha} = 1.96$;

 z_{β} = 1.28 for 90% power.

If the proportion of events in NexoBrid group is denoted by $p_1 = 0.64$

and the proportion of events in SoC group is denoted by $p_2 = 0.56$,

which are the observed proportions in the study MW2004-11-02, the number of subjects to be enrolled to achieve a power of 90% for the non-inferiority test is $n = \frac{2D}{p_1 + p_2} = 2164$ (1082 in each group).

Estimate based on study MW2010-03-02

Estimated log hazard ratio from study MW2010-03-02 (NexoBrid versus SoC) = 1.56, using a Cox proportional hazards model with shared frailty adjusted for center, age, %TBSA, proportion of the FT area of a patient and number of TWs (1,2,3-4, ≥5).

Standard error = 0.41

Target log hazard ratio = 1.56 - 0.41/2 = 1.36; target hazard ratio $\lambda = 3.90$.

The formula for total number of events D is: $D = \frac{4(z_{\alpha} + z_{\beta})^2}{(\ln \lambda)^2}$

(Piantadosi, Clinical Trials: A Methodologic Perspective, p.169)

 $z_{\alpha} = 1.96$;

 z_{β} = 1.28 for 90% power.

If the proportion of events in NexoBrid group is denoted by $p_1 = 0.62$

and the proportion of events in SoC group is denoted by $p_2 = 0.73$,

which are the observed proportions in the study MW2010-03-02, the number of subjects to be enrolled to achieve a power of 90% for the non-inferiority test is $n = \frac{2D}{p_1 + p_2} = 34$ (17 in each group).

Cosmesis and Function: MVSS at 12 months

Estimate based on study MW2004-11-02

Estimated difference in MVSS at 24 months from previous study (NexoBrid vs. SoC) = 3.32 - 3.83 = -0.51.

Standard error = 0.50

Target difference $\Delta = -0.51 + 0.50/2 = -0.26$.

The formula for the number of patients per group n is: $n = \frac{2(z_{\alpha} + z_{\beta})^2 \sigma^2}{q(\Delta - d_0)^2}$

where

 $z_{\alpha} = 1.96$;

 z_{β} = 1.28 for a power of 0.9;

 σ = the estimated common standard deviation= 2.33 (taken from previous study);

 d_0 = clinical equivalence level = 1.9;

q = proportion who are retained in follow-up to 12 months = 0.7 (assuming 30% loss to follow-up over 1 year)

For 90% overall power, the required sample size per group is 35 (70 overall).

Estimate based on study MW2010-03-02

Estimated mean MVSS at 12 months from study MW2010-03-02: NexoBrid 3.70; SoC 5.08

Standard errors: NexoBrid 0.24; SoC 0.38

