Difference: -1.38; Standard error of difference: 0.44

Anticipated difference: -1.38 + 0.44 / 2 = -1.16

The non-inferiority margin employed for this analysis is 1.9 score points.

Using a one-sided two-sample t-test with a significance level of 2.5%, 36 evaluable subjects are needed (18 in each group) to achieve a power of 90%. Using a conservative rate of missing values of 30%, the total sample sizes needed to achieve a power of 90% in the analysis is 52 (26 per group).

Note: In the analysis missing data will be imputed, leading to more evaluable subjects, increasing the power.

Cosmesis and Function: MVSS at 24 months

Estimate based on study MW2004-11-02

Estimated difference in MVSS at 24 months from previous study (NexoBrid vs. SoC) = 3.32 - 3.83 = -0.51.

Standard error = 0.50

Target difference $\Delta = -0.51 + 0.50/2 = -0.26$.

The formula for the number of patients per group n is: $n = \frac{2(z_{\alpha} + z_{\beta})^2 \sigma^2}{q(\Delta - d_0)^2}$

where

 $z_{\alpha} = 1.96$;

 z_{β} = 1.28 for a power of 0.9;

 σ = the estimated common standard deviation= 2.33 (taken from previous study);

 d_0 = clinical equivalence level = 1.9;

q = proportion who are retained in follow-up to 24 months = 0.5 (assuming 50% loss to follow-up over 2 years)

For 90% overall power, the required sample size per group is 49 (98 overall).

Estimate based on study MW2010-03-02

Since at this time the 24 months MVSS data of the MW2010-03-02 study is not yet available, the 12 months data will be used for the calculation.

Estimated mean MVSS at 12 months from study MW2010-03-02: NexoBrid 3.70; SoC 5.08

Standard errors: NexoBrid 0.24; SoC 0.38

Difference: -1.38; Standard error of difference: 0.44

Anticipated difference: -1.38 + 0.44 / 2 = -1.16

The non-inferiority margin employed for this analysis is 1.9 score points.

Using a one-sided two-sample t-test with a significance level of 2.5%, 36 evaluable subjects are needed (18 in each group) to achieve a power of 90%. Using a conservative rate of missing values of 50%, the total sample sizes needed to achieve a power of 90% in the analysis is 72 (36 per group).

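### Adverse-event tables for the later follow-up periods have no at-risk denominator and no person-time, so by default they understate new-event percentages as children leave follow-up

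*SAP*

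**What the plan says.** - **Statistic.** SAP Section 10.3.4.4 (Adverse Events): "Counts and frequencies of subjects reporting treatment emergent adverse events (TEAEs), related TEAEs, and serious TEAEs per treatment arm will be computed", by system organ class and preferred term. It states no denominator.
- **Periods.** The first-stage tables are split at the 12-week visit. The second part is "2) between the 12 weeks follow-up and the 12 months follow-up (including AEs from the first sub-period that are still ongoing"; a combined table to 12 months follows (also Section 11.1.5.4). Section 11.2.4.4 adds "adverse events occurring after the 12 months follow up", again with ongoing events carried in, and the entire study period.
- **Population.** Section 11.1.5 says of all safety variables, excepting only time to complete wound closure: "which will be evaluated using the FAS, will be evaluated on the safety set". Section 9.2: "The safety set includes all patients who received a treatment and analysis is focused on the treatment actually performed". Section 10.2: "Withdrawn subjects will be evaluated in the FAS and safety set".
- **Expected loss.** The only follow-up-loss figures are in the MVSS calculations of Section 13.3: "assuming 30% loss to follow-up over 1 year" and "assuming 50% loss to follow-up over 2 years".
- **Related rules.** Section 10.3.4.4 sets readmission and transfusion to missing for children who discontinue during the efficacy assessment period, except those lost to follow-up after completing eschar removal. It also sets antibiotic days to missing for early discontinuation and leaves children discharged early out of later vital-sign and pain analyses. Section 11.1.5.5 states the denominator for laboratory shift tables. The later AE tables have no rule of this kind.

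**The concern.** A percentage of subjects with a new event in a period is a risk estimate only if the children in the denominator could have been seen to have the event. Here the sole population rule carries every treated child into every period. A child who left at month 4 with no unresolved event adds one to the denominator for months 12 to 24 and can add nothing to the numerator. The result reads as a risk but is the risk multiplied by the share observed.

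The SAP sees this difficulty for readmission. It says that later events are unknown for children who discontinue, and that in the adult study MW2010-03-02 readmission was more common among those lost to follow-up than among the rest. Treating lost children as having no new event is therefore not plainly harmless. At stake is the absolute level of late AE, serious AE and local target-wound AE percentages, which readers will take at face value. There is also a practical gap: quality control is by double programming (Section 6.4), and two programmers could choose different denominators from this text.

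**Working it through.** **1. Check the loss inputs against the SAP's own figures.** Section 13.3 uses n per group = 2(z_α + z_β)²σ² / [q(Δ − d₀)²], with z_α = 1.96, z_β = 1.28, σ = 2.33, Δ = −0.26 and d₀ = 1.9.

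- The part without q: 2 × 3.24² × 2.33² / 2.16² = 24.43.
- 12 months, q = 0.7: 24.43 / 0.7 = 34.90, rounded up to 35 (stated: 35).
- 24 months, q = 0.5: 24.43 / 0.5 = 48.86, rounded up to 49 (stated: 49).

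So 0.7 and 0.5 are retained proportions, pooled over arms. If they applied to all 145 enrolled children, about 101 or 102 would remain at 12 months (145 × 0.7 = 101.5) and 72 or 73 at 24 months (145 × 0.5 = 72.5).

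**2. Months 12 to 24.** Assumptions: true 12-month risk of a new event 10%, constant hazard, retention falling linearly from 0.70 to 0.50, and loss unrelated to events. With t in years from month 12:

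- Hazard h = −ln(0.90) = 0.1054 per year; event-time density f(t) = h·exp(−ht).
- ∫f dt over the year = 0.1000; ∫t·f dt = [1 − (1 + h)·0.90] / h = 0.0491.
- Reported share on the full safety set = ∫(0.70 − 0.20t)·f dt = 0.0700 − 0.20 × 0.0491 = **0.0602**.

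Bounds that do not need the linear pattern: 0.10 × 0.50 = 5.0% and 0.10 × 0.70 = 7.0%.

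**3. 12 weeks to 12 months.** With linear loss reaching 30% at one year, retention at 12 weeks is 1 − 0.30 × 12/52 = 0.93. A true 10% risk in the period then shows as between 0.10 × 0.70 = 7.0% and 0.10 × 0.93 = 9.3%. Tables up to 12 weeks are little affected, and the combined tables only for late events.

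**4. Between arms.** Equal retention multiplies both arms by the same factor, so the risk ratio stays at 1.00. A hypothetical imbalance with the same true 10% risk, and what each remedy does to it:

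| Measure, months 12–24 | Retention 0.75→0.60 | Retention 0.65→0.40 | Ratio |
|---|---|---|---|
| Full safety set | 0.075 − 0.15 × 0.0491 = 6.76% | 0.065 − 0.25 × 0.0491 = 5.27% | 1.28 |
| At risk at period start | 6.76 / 0.75 = 9.0% | 5.27 / 0.65 = 8.1% | 1.11 |
| Events per 100 patient-months at risk | 100h / 12 = 0.88 | 0.88 | 1.00 |

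A start-of-period denominator alone therefore does not remove the distortion; the exposure-adjusted rate does under these assumptions.

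**5. Which dates can define being at risk.** Section 10.1.1 imputes a missing 12-month date as wound-closure confirmation plus 12 months. A child who left at month 4 would get a 12-month date after leaving and would count as at risk. A missing 24-month date becomes the study termination date, so that child's second period would end before it began. These imputed dates cannot define the risk set.

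**6. Carried-over events.** Ongoing AEs enter later periods, and missing AE end dates are imputed forward (Section 10.1.1). An early leaver with an unresolved AE can thus be in a later numerator. Steps 2 to 4 concern new-onset events only.

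**The case against.** The strongest reply is that the SAP never says the later tables divide by the whole safety set. That is right: the denominator follows from Sections 9.2, 10.2 and 11.1.5 together and is not written down. But no other population is offered, so it is the default.

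Second, a reader might infer that the SAP plans for 30% and 50% loss of AE follow-up. It does not. These are pooled MVSS sample-size inputs, and Section 13.3 calls the same rates conservative when it applies them to the second prior study. MVSS needs a blinded scar assessment, whereas the April 2020 memo (Section 13.4) allows AEs to be collected by telephone. Loss of AE information may well be smaller.

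Third, a reader might infer that every lost child counts as event-free. Carried-over AEs show otherwise, and they push the later percentages up. They do not recover unseen new events; they mix two kinds of event in one numerator.

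Fourth, no planned between-arm test uses these AE tables, second-stage testing is exploratory (Section 11.2.8), all AEs are listed, and a disposition table is planned. Scar quality, range of motion and readmission have their own analyses. All of this stands and limits the weight of the point. It does not correct the percentages themselves.

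**Conclusion.** The concern holds as a defect of the default method: later-period AE percentages keep children who can no longer contribute new events, and nothing in the SAP supplies an at-risk number or person-time beside them. The direction for new-onset events is downward. Its size depends on AE retention, which the documents do not give. At the MVSS retention assumptions, a 10% risk in months 12 to 24 would show as about 6% (5% to 7% without the linear pattern), and in 12 weeks to 12 months as 7.0% to 9.3%.

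A reader might go further and infer that the arm with more dropouts will look safer. The documents do not support that as a finding. They report no loss by arm, and with equal loss the ratio is 1.00. The 1.28 in the working rests wholly on invented retention figures. Because treatment is open, unequal retention cannot be excluded either, which is reason enough to report exposure by arm.

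**What to change.** Keep the safety-set tables as planned. For each AE sub-period after the 12-week visit:

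1. State the denominator and show the number at risk by arm, meaning children whose actual last-contact or study termination date is on or after the period start. Do not use the imputed visit dates of Section 10.1.1 for this.
2. Add exposure-adjusted rates by arm for all, serious and local target-wound-related treatment-emergent AEs: subjects with a new-onset event per 100 patient-months at risk. Time at risk stops at the first such event, the period end or the last contact, whichever comes first.
3. Count new-onset AEs separately from AEs carried over as ongoing, so that numerator and denominator cover the same children.

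The cost is SAP wording, a few derived variables (including a true last-contact date for each child) and extra table columns. Beyond that date, no new measurements are needed.

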	All subjects will be invited to one additional extended follow up visit that will occur at least 30 months after wound closure confirmation for a blinded assessment of cosmesis, function and QoL evaluation
Dosage and route of administration:	Two grams or 5 grams of NexoBrid sterile powder are mixed in 20 grams or 50 grams of sterile Gel Vehicle to obtain NexoBrid Gel. NexoBrid Gel is applied to the burn wound at a dose of 2g NexoBrid/20g Gel per 180cm² for four hours.
	In most cases, NexoBrid is effective after a single application; however it may be applied for a second time to the same burn area based on the investigator's judgment of debridement efficacy.
	NexoBrid should not be applied more than twice to the same burn wound area.
	NexoBrid should not be applied to more than 15% TBSA in one session.
	Inclusion Criteria- Patient level
	1. Stage 1: Males and females between 4 years to 18 years of age,
	Stage 2 (upon DSMB review): Males and females between 1 year to 18 years of age.
	Stage 3 (upon DSMB review): Males and females between 0 years to 18 years of age.
	2. Thermal burns caused by fire/flame, scalds or contact.
	3. Patient total burns area $\geq 1\%$ DPT and / or FT,
	4. Patient total burns area should be ≤ 30% TBSA; SPT, DPT and/or FT in depth,
Inclusion/ Exclusion Criteria:	5. Signed written informed consent by a legal guardian can be obtained within 84 hours of the burn injury.
	Inclusion Criteria - Wound level
	At least one wound (a continuous burn area which can be treated in one session; might include several anatomical areas) in a patient should meet all following criteria:
	 Wound that is ≥ 1% TBSA (DPT and/or FT) (not including face, perineal or genital),
	2. Wound is composed of DPT and/or FT in depth. Superficial partial thickness areas may be included in the wound area only if cannot be separated from deeper areas (e.g. surrounded by or mixed with DPT areas) and might interfere with the treatment of the deeper areas,
	3. Wound that is intended for surgical eschar removal,
	4. Wound's blisters can be unroofed, as judged by the investigator.

FINAL

Exclusion Criteria

- 1. Patients weighing less than 3kg,
- 2. Patients who are unable to follow study procedures and follow up period,
- 3. Patients with electrical or chemical burns,
- 4. Patient with a continuous burn area above 15% TBSA,
- 5. Patients with no DPT and/or FT burn area (only SPT wounds),

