7.2.3.4. Adverse Events

For each AE the following information will be determined:

- AE description
- Type of AE (General, Local TW related, Local not TW related)
- onset date and time
- outcome date and time
- outcome (resolved, resolved with sequelae, not resolved, death)
- intensity (mild, moderate, severe)
- action taken regarding study drug (yes, no)
- relation to study drug (not related, remotely related, possibly related, probably related, related)
- treatment required (none, medication, surgery, hospitalization, other)
- seriousness (serious, not serious)

Treatment-emergent Adverse Events (TEAEs) are defined as AEs that start during or after first NexoBrid or SoC treatment. TEAEs, related TEAEs, and Serious TEAEs will be summarized by Medical Dictionary for Regulatory Activities (MedDRA) system organ class, preferred term and severity. Events where the relation is considered "related", "possibly related", or "probably related" will be considered as related and events where the relation is considered 'not related' or 'remotely related' will be considered "not related". Events with missing causality will be considered as "related" and will be included in the summary of related TEAEs. Serious AEs resulting in death and AEs resulting in withdrawal from the study will be listed separately.

For randomized patients, AEs that occur between signing the informed consent document and receipt of study treatment will be provided in a listing.

Except for a summary table on event level, TEAEs will be reported on a per-patient basis. This means that even if a patient reported the same event repeatedly (i.e., events mapped to the same preferred term) during the assigned study period, the event will be counted only once in tabulations. In the latter case the event will be assigned the worst severity and the strongest relationship to the study drug. The earliest date will be regarded as start date of the event and

the latest date will be regarded as stop date of the event. All AEs, including those occurring more than once will be listed.

The same rules for counting, severity and relationship apply for PTs mapped to the same system organ class.

Notes:

- The MedDRA version will be denoted in the footnote of tables and listings.
- Listings will be sorted within patients by start date of the adverse event according to treatment group.

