11.1.5.4. Adverse Events

In this analysis, only the treatment emergent adverse events occurring until the 12 months follow-up visit will be analyzed.

All adverse events will be listed. Furthermore, the following tables will be produced separately for the following sub-periods: 1) until the 12 weeks follow-up, 2) between the 12 weeks follow-up and the 12 months follow-up (including AEs from the first sub-period that are still ongoing), 3) combined until the 12 months follow-up:

- Summary of Treatment Emergent Adverse Events (TEAEs) on a subject level and on an event level
- Summary of TEAEs by System Organ Class (SOC), and Preferred Term (PT) separately for:
 - All TEAEs

- Treatment related TEAEs
- o General and local, not TW-related TEAEs
- Local, TW-related TEAEs
- Summary of Special Interest TEAEs by PT (for sub-period 1), separately for:
 - TEAEs with PTs associated with fever (Pyrexia, Body Temperature Increased, Hyperthermia)
 - TEAEs associated with target wound infections (only if Local, TW-related: relevant preferred terms will be reviewed after finalization of coding and can include for example preferred terms as: Wound Infection Bacterial, Staphylococcal Skin Infection, Wound Infection, Wound Infection Staphylococcal if reported as local TW-related)
 - TEAEs associated with target wound pain (relevant preferred terms will be reviewed after finalization of coding)
- Summary of TEAEs by SOC, PT, and time of onset (for sub-period 1) separately for:
 - o All TEAEs
 - General and local, not TW-related TEAEs
 - Local, TW-related TEAEs
 - All Treatment Emergent Serious Adverse Events (TESAEs)
- Summary of TEAE by SOC, PT and maximum intensity. In this table, patients who
 experienced multiple AEs with the same PT, but different intensities will be counted
 only once per PT with their maximum intensity. Subjects with multiple AEs with the
 same SOC but different intensities will be counted only once per SOC with their
 maximum intensity in the SOC row. This table will be produced separately for:
 - All TEAEs
 - Treatment related TEAEs
 - General and local, not TW-related Treatment related TEAEs
 - o Local, TW-related Treatment related TEAEs
 - All TESAEs
 - Treatment related TESAEs

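### The adverse-event onset tables use a treatment session whose length depends on treatment, so their time windows are not aligned between the arms

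*SAP*

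**What the plan says.** SAP 10.3.4.4, under Adverse Events, sets six onset categories, beginning "Time of onset (during the treatment session / within 24 hours after treatment" and continuing with 24 to 72 hours, 72 hours to the end of week 1, weeks 2 to 4, and beyond 4 weeks. A note fixes the first category: "During the treatment session is defined as the time frame from start date/time of first eschar removal procedure to end date/time of last eschar" (that is, of the final procedure). No note says when *after treatment* begins.

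SAP 11.1.5.4 uses the categories in one family of tables, "Summary of TEAEs by SOC, PT, and time of onset (for sub-period 1) separately for" all TEAEs, general and local events not related to target wounds, local target-wound events, and serious TEAEs. Sub-period 1 ends at the 12-week follow-up. SAP 11.1.12 repeats the adverse-event analyses for this sub-period by age group, as deemed relevant.

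Other safety definitions use the first treatment as their anchor. SAP 7.2.3.4: "Treatment-emergent Adverse Events (TEAEs) are defined as AEs that start during or after first NexoBrid or SoC treatment". The PTT/INR change in 10.3.4.4 is likewise taken 4 hours after first treatment in both arms.

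**The concern.** The session is bounded by the first and last procedures, so its length is known only after treatment has run its course. The SAP foresees very different courses (10.3.3.2.5): a single NexoBrid application, NexoBrid followed by non-surgical or surgical procedures, one surgical procedure, or an alternation of surgical and non-surgical procedures. An event on day 5 is in-session for a patient whose course lasts a week, but belongs to the 72-hours-to-week-1 category for a patient cleared on day 0.

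Two things are at stake. First, the arms can show different onset profiles with no difference in event rates. Second, in any patient with several procedures, a reaction in the first hours is pooled with events from days later, which blurs the acute signal an onset table is meant to show.

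The term is also used inconsistently. The Protocol synopsis (dosage) and the blood-culture footnotes in SAP 7.1 and 7.2.3.6 use *session* for a single application. SAP 11.1.5.8 has a separate term, the ER period, in its transfusion summaries. A reader of the onset table could easily take the in-session column to mean during the application.

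**Working it through.** The documents give no figure for the onset tables and no first-to-last duration, so there is nothing of the plan's own to reproduce. The check shows what the definition does under stated assumptions.

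**Inputs from the documents**
- One application: "2g NexoBrid/20g Gel per 180cm² for four hours" (Protocol synopsis, dosage). A repeat is possible: "it may be applied for a second time to the same burn area based on the investigator's judgment of debridement efficacy".
- Surgical excision in earlier studies: NexoBrid 0.42 and SoC 0.80 in MW2004-11-02 (SAP 9.1.2); NexoBrid 0.04 and SoC 0.72 in MW2010-03-02 (SAP 13.3).
- Expected direction: the primary hypothesis is earlier complete eschar removal with NexoBrid (SAP 7.2.2.1). The design log hazard ratio is -1.39 for SoC versus NexoBrid (SAP 9.1.1), and exp(1.39) = 4.0. That clock starts at randomization, not at the first procedure, so it supports the direction only indirectly.

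**Assumptions**
- The same constant rate in both arms, 0.05 events per patient-day.
- A short course lasts 4 hours in either arm; a long course lasts 3 or 7 days.

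**Step 1: chance of at least one in-session event, 1 - exp(-0.05 × L), L in days**
- 4 hours: 1 - exp(-0.05 × 4/24) = 0.8%
- 3 days: 1 - exp(-0.15) = 13.9%
- 7 days: 1 - exp(-0.35) = 29.5%

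**Step 2: mix short and long courses within an arm**

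| Arm and mix | Long course 3 days | Long course 7 days |
|---|---|---|
| NexoBrid, none long | 0.8% | 0.8% |
| NexoBrid, 4% long | 1.4% | 2.0% |
| NexoBrid, 42% long | 6.3% | 12.9% |
| SoC, 50% long (assumed) | 7.4% | 15.2% |
| SoC, all long | 13.9% | 29.5% |

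Example: 0.42 × 29.5% + 0.58 × 0.8% = 12.9%. The 4% and 42% borrow the earlier excision rates as the share of NexoBrid patients with a long course. With 7-day long courses, the contrast with no true difference runs from 0.8% against 29.5% to 12.9% against 15.2%.

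**Step 3: where the later windows fall**

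If *after treatment* starts at the end of the last procedure, the within-24-hours window covers these days since the start of the first procedure:
- 4-hour session: days 0.17 to 1.17
- 3-day session: days 3 to 4
- 7-day session: days 7 to 8

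With onsets spread evenly over 35 days (assumed), this window holds 1/35 = 2.9% of them in all three cases, while the in-session share moves from 0.5% to 8.6% to 20.0%. If the event rate falls with time instead, the later windows also diverge, and the arm with the shorter sessions shows more events in them.

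**Step 4: the same data anchored to the first procedure**

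Under the even spread, 0 to 24 hours holds 1/35 = 2.9% of onsets, 24 to 72 hours 2/35 = 5.7%, and 72 hours to day 7 4/35 = 11.4%, whatever the session length and in either arm.

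**The case against.** The definition is worded identically for both arms, and no between-arm test is planned on these tables. NexoBrid courses can be long: a second application is allowed, later procedures are foreseen, and 42% of NexoBrid patients in MW2004-11-02 had excision. SoC courses can be short, since one surgical procedure is a listed course. A reader might infer that the tables compare hours in one arm with days in the other. The documents do not support that: no durations are given, and both arms can contain both kinds of course.

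A reader might also infer that the tables favour NexoBrid. A longer SoC session enlarges the SoC in-session column, but it also takes early SoC events out of the first post-treatment columns, where early NexoBrid reactions then stand out. Events move between columns, and the direction depends on the column read.

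Nor is acute safety visible only here. Fever, target-wound infection and target-wound pain have their own tables (11.1.5.4). Vital signs and pain are summarised over the first seven daily assessments, and pain also before and after procedures (11.1.5.6, 11.1.5.7). Laboratory values are given per procedure (11.1.5.5), INR and PTT after first treatment (11.1.5.14), and all adverse events are listed.

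These arguments limit the size and reach of the point. They do not align the windows, and they do not supply the missing starting point.

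**Conclusion.** The point holds in limited form. The session definition makes the first onset category, and by inference the start of every later one, depend on how treatment went. The onset tables for sub-period 1 therefore do not compare the arms over the same time since first treatment, and they pool early with late events in patients with several procedures.

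Three elements are inference or assumption. The end of the last procedure as starting point is inferred, because the SAP is silent. The shorter average session with NexoBrid is an expectation drawn from the primary hypothesis and the prior excision rates. The event rate, the long-course lengths, the 4-hour length of a short SoC course and the SoC mix are all assumed. Within those assumptions the artefact could be large or small, and the documents do not say which.

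Only one family of descriptive tables is affected. Overall TEAE, severity, relatedness and serious-event counts do not use these windows.

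**What to change.** In SAP 10.3.4.4:
- Tabulate onset in both arms from the start date/time of the first eschar removal procedure, in fixed windows: 0-24 h, >24-72 h, >72 h to day 7, weeks 2-4, >4 weeks.
- Flag separately the events that start during, or within 24 hours after, an individual procedure.
- Report first-to-last procedure duration by arm.
- If the session-based table is kept, state the starting point of its *after treatment* windows, and reconcile the term with its use for a single application elsewhere.

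The cost is small: one more derived variable and one more table. SAP 7.2.3.4 already records onset date and time, and the existing definition already relies on procedure start and end times. The drawback is that reactions to a later application or excision are spread over the fixed windows; the individual-procedure flag recovers them. Anchoring to the first procedure aligns time since first treatment, but not time since the burn, which can still differ between the arms.
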